In summary, the study aims at the definition of survival, toxicity and QoL data in a representative sample of intermediate, high and very high risk prostate cancer patients consecutively recruited in Italian Radiation Oncology Centres over two years. Parameters considered will be OS, CSS and bRFS, toxicity (rectal, bladder, bowel toxicity, according to CTCAE v.4 scale) and QoL (according to the SF-12 scale and UCLA-PCI scale). Primary end point will be OS. Secondary endpoints will be CSS, bRFS, gastrointestinal and genitourinary toxicity, QoL deterioration.

Study Design

This is a prospective, multicenter, observational cohort study aimed to describe the advantage/disadvantage of different treatments of patients with intermediate/high/very high risk prostate cancer, through a web-based database.

Study Duration

The recruitment period, taking into account the needed sample size (*v.infra*) will be of two years, followed by three-year follow up period for each patient, with an accrual of at least 400-500 patients.

Population, Procedures

The study will include all consecutive patients affected by intermediate, high or very high-risk prostate cancer that fit the inclusion criteria and who are evaluated at each Centre involved in the study. Patients may have already undergone or not to radical prostatectomy and/or pelvic lymphadenectomy.

Inclusion criteria

- Men older than or aged 18 years;
- Histologically confirmed intermediate, high or very high risk prostate cancer patients (NCCN classification: Intermediate Risk T2b and T2c or Gleason Score 7 or PSA value between 10 and 20 ng/mL; High risk: T3a or Gleason score 8-10 or PSA > 20 ng/ml; Very high risk: T3b-T4 or patients with multiple adverse risk factors reported in the high risk category that may be shifted in the very high risk group
- Patients eligible for -and actually submitted to- radical radiotherapy treatment (+/- androgen deprivation) or adjuvant radiotherapy treatment after surgery (radical prostatectomy +/- pelvic lymphadenectomy);
- No other synchronous or previous malignant tumor other than skin basal cell carcinoma;
- Patients able to understand and sign the appropriate informed consent;
- Patients able to fill the QoL questionnaire;

Exclusion criteria

- Patients aged less than 18;

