Centers involved will identify all the eligible cases with biopsy proven prostate adenocarcinoma. Patients who are candidate to get involved in the study will be contacted by the physician in charge of the study for each Center. **Every** prostate cancer patient consecutively evaluated at the recruiting Centers and planned to receive radical exclusive or post-operative radiotherapy will be registered; this registration includes demographic and staging results data; only intermediate, high, very high patients will have, however, treatment and follow up CRF compiled (both treated with or without ENI; +/- ADT).

Eligible patients will then receive all the information necessary to formulate their adhesion to the study and finally the physician will fill in the “Pretreatment” Case Report Form (CRF) that will include:

- Demographic Information (date of birth, study title, civil state, working information);
- Another person (relatives, friends,...) as a contact to minimize follow up loss;
- Anamnestic data (height, weight, smoking habit, comorbidities, Cumulative Illness Rating Scale [44], Attachment 1);
- Initial diagnosis (date; PSA at diagnosis);
- Risk factors;
- Staging (clinical TNM, date of biopsy, Gleason score, total number of samples, number of positive samples);
- Quality of life and symptoms caused by prostate cancer (using Italian UCLA Prostate Cancer Index) [45, 46];
- General quality of life (SF-12 Standard V1) [47].

The choice of the treatment will be done based on commonly used international guidelines and on the specific internal protocol of each participating Center.

Since this study is observational, involved patients will be treated following *good clinical practice* and institutional policies procedures.

Clinical outcomes, (such as overall survival and biochemical relapse free survival) and variables, demographic features, dosimetric analysis and acute/late toxicities of both RT and ADT will be reported.

Phase 3: Follow-up (1, 3, 6, 12, 18, 24, 30, 36 months)

After the end of the radiotherapy treatment patients will be evaluated 1, 3, 6, 12, 18, 24, 30 and 36 months since the last session.

Every patient will be contacted by the physicians to fill a CRF that will include:

- Vital state (mortality, date and causes of death) or loss to follow up;
- Last PSA value;

- Other treatments (drugs);

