- Treatment : type of treatment, start date, PSA value before treatment; if surgery type of surgery and pathological TNM, margins, Gleason Score, number of positive lymph nodes; if external RT (intent, modality, technique, dose/fraction, volumes, concomitant hormonal therapies); if brachytherapy (type, intent, dose); if hormone therapy (type of drugs, start and end date, total duration);
- Acute and late toxicities;
- Biochemical Relapse with PSA value and date of last PSA;
- Quality of life and symptoms due to prostate cancer (Italian UCLA-PCI);
- General quality of life SF-12.

Toxicity and response evaluation

The enrolled patients will undergo the first follow up visit one month after the end of radiotherapy. On that occasion, clinical examination will be performed and previously prescribed blood tests, if required, will be evaluated. Genitourinary and gastrointestinal toxicity due to radiation therapy for prostate cancer will be reported according to the NCI Common Terminology Criteria for Adverse Events (CTCAE) version 4 for adverse event (AE) reporting. The CTCAE version 4 is identified and located on the CTEP web site at:

http://ctep.cancer.gov/protocolDevelopment/electronic_applications/ctc.htm [48]

In addition, a Case Report Form (CRF) will be completed (see Attachment 2), regarding:

- Technical characteristics of the radiation treatment (dose, volume, technique, association or not with hormonal therapy);
- Quality of life and complications due to prostate cancer (according to Italian UCLA-PCI) [45, 46];
- General quality of life (SF-12 Standard V1) [47].

Thereafter patients will be evaluated at 3-months, 6-months and 12-months after the end of radiotherapy, and then every 6 months for at least 24 months. During all those scheduled follow up visits, PSA level (jointly with testosterone, in case of association with hormonal therapy) and

previously prescribed blood texts if required, will be evaluated. Patients will undergo clinical examination, and genitourinary and gastrointestinal toxicity will be assessed according to the CTCAE v4.0 classification scale). In addition, a CRF (see Attachment 3) will be completed at each visit, regarding:

- Survival status (mortality, date and cause of death) or exit from the study;
- If macroscopical recurrence or disease progression occurred, the radiological exams (if performed);
- Further treatments received/planned after radiotherapy;
- The last available PSA;

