- Quality of life and complications due to prostate cancer (Italian UCLA-PCI) [45, 46];
- General quality of life (SF-12 Standard V1) [47].

The Italian UCLA-PCI and SF-12 Standard V1 questionnaires reported in Attachment 2 and Attachment 3 [45, 46, 47] will be given by the referring physician and self-compiled by patients in physician's absence, eventually with the help of a nurse if necessary; thereafter, the referring physician will insert the data to the database.

Data Collection, Confidentiality

Data will be collected through an *ad hoc* web based software, built to guarantee:

1. Respect of the Italian laws and of the international rules about GMP and privacy, according also to the general principles fixed by the Helsinki declaration and its subsequent updates;
2. The anonymization of the patient records;
3. The possibility for each participating Center to have unrestricted access to its own data;
4. The restriction of the access to the full dataset composed by the sum of the records provided by the single Centers; this will be allowed only after the authorization of the PI and the Study Coordinator. Once the study will be completed, access to the whole database will be possible only after having obtained the authorization of the AIRO President in charge and of the AIRO Board;
5. The safe storage of the data, along with that of the previous AIRO-PCSG studies, along with.

The use of the software will be elucidated to the single participating Centers in *ad hoc* start up

meetings, to guarantee an appropriate and homogeneous data collection; a tool bar will however be devised, to automatically verify inconsistencies in the data collected.

Statistical Considerations

Sample size

From previous experiences of the AIRO PCSG [49, 50], at least 15-20 Radiotherapy Centers from different regions of the country will be able to participate to the study. It is conceivable an accrual of at least 400-500 patients within 2 years and a further follow up of at least 3 years for each patient. For intermediate and high risk patients, an overall survival at 5 years of 0.8 has been previously reported (RTOG 94-13) [51]. According to the primary end-point of the study, a sample size of 400 patients will allow to estimate a 5-year survival of 0.8 with 95% confidence interval of 0.76-0.84 [52].

Statistical Analyses

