In order to describe the data, mean and standard deviation will be used for normally distributed continuous variables, median and ranges for non-normally distributed continuous variables, proportions and percentages for categorical variables. Associations between two categorical variables will be assessed through the Pearson's chi-squared test or Fisher test, when appropriate. Differences between two-sample central tendencies will be assessed with a two independent sample t-test or Mann-Whitney U test or Wilcoxon, depending on distribution of the continuous variable.

Analysis of variance and covariance and regression models will be used for evaluating the associations of some variables with survival taking account of possible confounders.

In order to compare groups in terms of survival end-points, Kaplan-Meier curves will be estimated and log-rank tests will be performed.

Periodical analyses are planned in order to check the quality of entered data.

The analyses will be performed by using STATA 13 (StataCorp. 2013. Stata Statistical Software: Release 13. College Station, TX: StataCorp LP) or SPSS Statistical Software.

Ethical committee

After the final approval by the AIRO-PCSG, the Protocol will be submitted to the Ethical Committee (EC) of the Study Coordinating Centre; when it will be approved, the single participating Centres will consequently apply for approval of their EC. According to the judgment of the PI and of the Study Coordinator, the first patient will be enrolled when a sufficient number of Centres will have obtained EC approval. This will be the starting date for the study.

The present study will be performed in accordance with the present protocol, with the principles of Good Clinical Practice in the respect of the ICH GCP guidelines and the ethical principles contained in the Helsinki declaration.

Publication rules

Interim and final results of the study will be published under the final responsibility of the PI and of the Study Coordinator.

The following publication rules will be enforced:

1. The participating Centers should approve the paper;
2. Only Centers contributing to more than 5% of the cases collected will have a person quoted as Author of the paper; however, every Center contributing to the common database, as well as the people working to realize the Study, will be publicly quoted and their contribution acknowledged in the paper;
3. Authorship is granted in proportion to:
 - a. the cases contributed to the database;

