ATTACHMENT 3 – 3, 6, 9, 12, 18, 24, 36 MONTHS FOLLOW UP

	
1 He does not adhere anymore for health reasons, specify _____
 
2 He is not interested anymore to take part in the study
 
3 He is not traceable

Does the patient still undergo Hormonal Therapy?	
1. Yes
 
If yes: (FILL IN POINT 4 BELOW)
 
0 No
 
If no: Date of ending hormonal therapy  / /  day month year

Has he developed new comorbidities? (It is possible to fill in more than one option)	
0 . No
 
1 . Yes
 
If yes:
 
 1 Cardiac (specify _____) 2 Vascular (including hypertension) 3 Pulmonary (specify _____) 4 Eye, ear, nose, throat, larynx 5 Gastro-intestinal (specify _____) 6 Hepatic (liver only) 7 Renal (kidneys only) 8 Musculo-skeletal (specify _____) 9 Intertegumentary (skin) 10 Neurological (specify _____) 11 Endocrine-metabolic (specify _____) 12 Cognitive-psychiatric, behaviour 13 Genito-urinary (ureter-genitals) (specify _____) 14 Other malignancies (including Haematopoietic malignancies)

	15 Other, specify _____	
Has he undergone further treatments for prostate cancer, subsequent to those reported in Attachment 1 (1-month follow up)?	0 No	
	1 Yes	
	If yes:	
	1	Surgery
	2	External Beam Radiation Therapy
	3	Brachytherapy
	4	Radiometabolic Therapy
	5	Hormonal Therapy
	6	Focal Therapy
7	Chemotherapy	
8	Others, specify _____	

If he has undergone further treatments, specify:

Date of starting the new treatment |__|/|__|/|__|_|_|

day month year

PSA before starting the new treatment |__|_|_|_|. |__|_|_| ng/mL

 External Beam Radiotherapy	
Aim of Radiotherapy	1 Palliative
	2 Other, specify_____
Modality	1 IGRT
	2 Non IGRT
Technique	1 3D-CRT

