	2 IMRT
	3 SBRT (stereotactic body radiotherapy)
If palliative Radiotherapy, site	1 Bone lesions

	2 Nodal lesions
	3 Visceral metastases
	4 Pelvic lesions
	5 Others
Dose/fraction	__ __ , __ __ Gy
Total dose	__ __ , __ __ Gy
Association with Hormonal Therapy	
 1 Radiotherapy alone 2 Radiotherapy and neoadjuvant Hormonal Therapy (before RT) 3 Radiotherapy and adjuvant Hormonal Therapy (after RT) 4 Radiotherapy and neoadjuvant + adjuvant Hormonal Therapy
2 Brachytherapy	
Type of brachytherapy	
 1 LDR (internal radiation therapy) 2 HDR
Aim of brachytherapy	
 1 Exclusive 2 Other, specify_____
3 Radiometabolic Therapy	
If yes	
 1 With alfa-emittent particles 2 Other, specify _____
4 Hormonal Therapy	
Type of Hormonal Therapy	
 1 ADT 2 Antiandrogen

If antiandrogen, specify the type:

- 1 Ciproterone acetate
- 2 Bicalutamide
- 3 Flutamide
- 4 Other, specify _____

If antiandrogen, specify the dose:

- 3 LHRH-Agonist (or GnRH)
- 4 LHRH-Antagonist (or GnRH)
- 5 Other, specify _____

The used drugs _____

5 Focal Therapy

Type of Focal Therapy	1 High Intensity Focused Ultrasound
	2 Cryotherapy
	3 Other, specify _____

Aim of Focal Therapy	1 Curative
	2 Palliative
	3 Other, specify _____

6 Chemotherapy

Type of drug	_____
--------------	-------

Treatment scheme

7 Second line Hormonal Therapy

Type of drug	_____
--------------	-------

Treatment scheme

Has he planned further treatments related to prostate cancer, subsequent to those reported in Attachment 1 (1-month follow up)?
	
0 No
 
1 Yes, specify: If yes:
 
1 Surgery
 
2 External Beam Radiation Therapy
 
3 Brachytherapy
 
4 Radiometabolic Therapy
 
5 Hormonal Therapy
 
6 Focal Therapy
 
7 Chemotherapy
 
8 Others, specify _____

If he does not have undergone further treatments, is he able to remember the last PSA value?
	
1 Yes If yes: PSA _____ ng/mL Date of the PSA value test _____ / _____ / _____ day month year
 
0 No If no: Does he agree to ask it to his family doctor? 0 No 1 Yes What is his family doctor's name? _____
 
PSA referred by the family doctor _____ ng/mL Date of the PSA value test referred by the family doctor _____ / _____ / _____ day month year

References

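### The plan does not ask for vital status after a man exits, including exit for health reasons; if such men are censored at exit, overall survival may be overstated

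*Combined protocol and SAP*

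**What the plan says.** - **Endpoint and analysis.** The summary under Aims of the study states: "Primary end point will be OS". Under Statistical Analyses, groups are compared on survival as follows: "Kaplan-Meier curves will be estimated and log-rank tests will be performed". Neither place gives a censoring rule.
- **What follow-up records.** The Phase 3 list has "Vital state (mortality, date and causes of death) or loss to follow up". The Toxicity and response evaluation section, describing the Attachment 3 form, has "Survival status (mortality, date and cause of death) or exit from the study". The synopsis (Visits and exams) carries both items.
- **Exit reasons.** Attachment 3 has three separate codes. The first is "He does not adhere anymore for health reasons, specify"; the other two are loss of interest and being untraceable.
- **Safeguards.** The pretreatment form in Phase 2 collects "Another person (relatives, friends,...) as a contact to minimize follow up loss", and Attachment 1 has fields for that person's phone number. Attachment 3 also asks "What is his family doctor's name", but only to obtain a PSA value that the patient cannot recall.
- **Precision.** Under Sample size: "a sample size of 400 patients will allow to estimate a 5-year survival of 0.8 with 95% confidence interval of 0.76-0.84".

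**The concern.** Kaplan-Meier and log-rank methods treat a censored man as having the same future risk as those still followed. A man who drops out because he is ill probably does not. If his record stops at exit, his later death is missing from the primary endpoint and the survival curve is pulled upward. A larger sample does not reduce this error, and the stated confidence interval does not cover it.

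The information is also hard to recover. If nobody asks about these men while the study runs, the analyst has no deaths to restore at the end. Not-traceable exits leave the same gap. Exit rates may differ between men treated with and without ENI or ADT, so group comparisons could be distorted as well as the overall estimate. Toxicity is graded at scheduled visits, so late toxicity in men who no longer attend would go unseen too.

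**Working it through.** **1. The plan's own interval.** Inputs from Sample size: n = 400, 5-year survival p = 0.8. The Wald half-width is 1.96 × √(0.8 × 0.2 / 400) = 1.96 × 0.02 = 0.0392, giving 0.761 to 0.839. This reproduces the stated 0.76-0.84. The calculation treats every man's status as known and covers sampling error only.

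**2. What happens after exit.** The Phase 3 list and the Toxicity and response evaluation section each join survival status to exit or loss with an "or" in a single item. The Phase 2 list collects a contact person for the general purpose of limiting loss. No sentence links that contact to vital status after an exit, defines a date last known alive, or distinguishes stopping visits from refusing all further data.

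**3. Size at 36 months. All inputs here are assumptions.**
- Survival at 36 months in men still followed is 0.90, so the hazard is h = −ln(0.90)/3 = 0.0351 per year and 3h = 0.1054.
- A fraction f is assigned an exit time uniform over 0-3 years. The hazard is h before exit and k × h after it.
- Kaplan-Meier with censoring at exit estimates 0.900, because everyone under observation has hazard h.
- True survival is (1 − f) × 0.900 + f × M, where M = 0.9^k × (0.9^−(k−1) − 1) / ((k − 1) × 0.1054).
- k = 3: M = 0.729 × 0.2346 / 0.2107 = 0.811.
- k = 8: M = 0.4305 × 1.0908 / 0.7375 = 0.637.
- The overstatement is f × (0.900 − M), in which 0.900 − M is 0.0885 for k = 3 and 0.2634 for k = 8.

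| Assigned to exit (f) | k = 3 | k = 8 |
|---|---|---|
| 5% | 0.4 points | 1.3 points |
| 10% | 0.9 points | 2.6 points |
| 15% | 1.3 points | 4.0 points |

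At f = 10% among 400 men, this means about 5.5 of 43.5 deaths (k = 3) to 12.5 of 50.5 deaths (k = 8) go unrecorded. With k = 1 there is no bias.

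**4. A second model on the plan's 5-year scale.** Take true 5-year survival of 0.80 with constant hazard, and let a share q of deaths follow directly on an exit and never be recorded. Kaplan-Meier then estimates 0.80^(1−q).
- q = 5%: 0.809, bias +0.9 points.
- q = 10%: 0.818, bias +1.8 points.
- q = 20%: 0.836, bias +3.6 points.

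The bias equals the 3.9-point half-width when 1 − q = ln(0.8392)/ln(0.80) = 0.786, that is q ≈ 21%, or about 17 of the 80 deaths expected among 400 men. This is a limiting case, because it places death immediately after exit.

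**5. Yardstick.** The bias in step 3 is at 36 months and the plan's half-width is at 5 years, so they are not directly comparable. At 36-month survival of 0.90 with n = 400, the half-width is 1.96 × √(0.9 × 0.1 / 400) = 0.029, or 2.9 points.

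**The case against.** A reader might infer that the form closes a man who leaves for health reasons and asks nothing more about him. The documents do not say so. Closure is read into the word joining the two items, and nowhere is a later death barred from entry. The top of Attachment 3, including the label above the exit codes, is missing from the available text. The protocol says this form records survival status, so no claim can be made that it lacks such a field. The three exit reasons have separate codes, so exits by reason can already be tabulated. Follow-up is described as physicians contacting every patient, and a second contact is collected expressly to limit loss. All of this stands.

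It is also tempting to say that these men are censored just before death. The 36-month model does not show that: among men who do exit, 14% (k = 3) to 33% (k = 8) die by month 36, and median survival after exit is ln 2 / (k × 0.0351) = 6.6 to 2.5 years. Nor can one say that the bias favours ENI or long-term ADT, because that depends on which group loses more ill men, and the documents do not address it.

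The objection does not supply the missing rule. An intention to limit loss is not an instruction to seek vital status after a recorded exit, and the protocol text is silent on that whatever the form's lost rows contain.

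**Conclusion.** The point holds as an omission affecting the primary endpoint. Survival status and exit are listed as alternatives, health-related exit is foreseen, and no legible text requires vital status afterwards or says how such men are censored. If they are censored at exit and die at a higher rate afterwards, overall survival is overstated. That is likely in direction but is not a demonstrated fact.

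Under the 36-month assumptions above, the overstatement runs from about 0.4 points (5% exit, 3-fold hazard) to about 4.0 points (15% exit, 8-fold hazard). Exit rate, post-exit hazard and 36-month survival are all assumed; the documents give none of them, so the true size cannot be determined. The change is worth making because it is cheap and deaths not collected cannot be restored in analysis.

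**What to change.** 1. In the protocol and on the follow-up form, separate stopping visits or questionnaires from withdrawing consent to all data.
2. For health-reason and not-traceable exits, keep recording vital status, date last known alive, and date and cause of death at the remaining scheduled time points, through the contact person already collected. Stop only if consent to this is withdrawn.
3. State in the Statistical Analyses section that men not known to have died are censored at the date last known alive.
4. Report exits by reason and by ENI/ADT group, and add a sensitivity analysis for health-related exits, for example varying their assumed hazard after exit.

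**Cost.** A few phone calls per time point, a form change and a short protocol addition. The consent text must cover contact after exit; the consent pages were not available, so whether it already does cannot be judged. The family doctor should not be counted on as a contact already held, since the name is requested only in one branch of the PSA item and with the patient's agreement. Complications reported by relatives should not be treated as CTCAE grades, so this change mainly protects survival and does little for the toxicity data.
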